7.8.3 Vital signs

An MMRM analysis for heart rate over time will be provided based on OC-AD on the randomised set and OC-OT on the treated set imputations. The model will follow the MMRM analysis described in [Section 7.6](#).

7.8.4 Electrocardiogram (ECG)

Clinically relevant abnormalities found at physical examination or ECG at Visit 2 will be considered to have already existed prior to signing of informed consent and therefore should be considered baseline conditions instead of adverse events, unless there is good reason to assume that they first appeared after signing of consent.

Outcomes of ECGs will be part of the reporting of medical history or AE reporting. Categorical findings as collected in the eCRF will also be summarized descriptively..

7.8.5 Others

Frequency of pregnancies and pregnancy outcomes will be listed by treatment.

Results of the Modified Rankin Scale will be summarized descriptively.

9. ADDITIONAL SECTIONS

9.1 REGIONS AND COUNTRIES

Countries will be assigned to regions following the assignment of the IRT system, which is outlined in Table 9.1:1. Listed countries include currently planned backup countries.

Table 9.1: 1 Regions and countries

Region	Country
Asia	China Japan Korea Singapore
Europe	Belgium Bulgaria Czech Republic Denmark Germany Hungary Italy Netherlands Poland Spain Romania Sweden UK
Latin America	Argentina Brazil Colombia Mexico
North America	Canada US
Other	India Australia South Africa Turkey

9.2 CONCOMITANT MEDICATION

Definitions of medication groups (such as ARBs, diuretics) will be based on World Health Organization Drug Dictionary (WHO DD) and will be stored in the PDMAP.

9.3 ADDITIONAL SUB-GROUP ANALYSIS FOR REGIONAL SUBMISSIONS

Disposition and demographics of the subpopulation for patients from USA and subgroup analyses for patient from the USA vs non-USA will be included in the appendix of the CTR. Efficacy endpoints evaluated will be primary endpoint, time to cardiovascular (CV) death, time to first HHF, HHF (first and recurrent) and renal slope. Safety will be summarized for patients from the USA.

Additional country or region-specific analyses will be conducted for patients from Mexico, East-Asia (China, Japan and Korea), China, Japan, Korea and India to be included into the country-specific submission documents as also outlined in [\(15\)](#). Primary endpoint, time to cardiovascular (CV) death, time to first HHF, HHF (first and recurrent) and renal slope will be presented. Main adverse event overviews, disposition, demographics will be presented.

9.4 INTERIM ANALYSES

An interim analysis will be conducted by the DMC as outlined in the CTP. If based on the interim analysis it is decided to stop the trial for overwhelming efficacy, all analyses belonging to the confirmatory testing strategy as described in this TSAP will be conducted on the snapshot as used for the interim analysis done by the DMC. All other analyses will be conducted on the final database lock.

2. LIST OF ABBREVIATIONS

Term	Definition / description
ACE	Angiotensin Converting Enzyme
AE	Adverse event
AESI	Adverse event of special interest
ALT	Alanine transaminase
ANCOVA	Analysis of covariance
ARB	Angiotensin Receptor Blocker
ARNI	Angiotensin Receptor blocker-Neprilysin Inhibitor
ASA	Acetylsalicylic acid
AST	Aspartate transaminase
ATC	Anatomical-Therapeutic-Chemical
BI	Boehringer Ingelheim
BicMQ	Boehringer Ingelheim customized MedDRA Query
BMI	Body mass index
BP	Blood pressure
CCB	Calcium channel blocker
CEC	Clinical Event Committee
CI	Confidence interval
CIF	Cumulative Incidence Function
CKD-EPI	Chronic Kidney Disease Epidemiology Collaboration
CRF	Case report form
CRT	Cardiac resynchronisation therapy
CTP	Clinical Trial Protocol
CTR	Clinical Trial Report
CV	Cardiovascular
DBL	Data base lock
DBP	Diastolic Blood Pressure
DKA	Diabetic ketoacidosis
DM	Diabetes mellitus
DM&SM	Data Management and Statistics Manual
ECG	Electrocardiogram
eCRF	Electronic Case Report Form

Term	Definition / description
eGFR	Estimated glomerular filtration rate
EMA	European Medicines Agency
EoT	End-Of-Text
EOT	End of treatment
EQ-5D	EuroQoL 5 dimensions
EudraCT	European Clinical Trials Database
FG	Fasting glucose
FU	Follow-up
GI	Gastrointestinal
HbA _{1c}	Glycosylated haemoglobin
HCRU	Health Care Resource Utilisation
HDL-C	High density lipoprotein cholesterol
HF	Chronic Heart Failure
HHF	Hospitalisation for heart failure
HLT	High level term
hsTnT	high-sensitivity troponin T
HR	Hazard ratio
ICD	Implantable Cardioverter Defibrillator
ICH	International Conference on Harmonisation
IPD	Important protocol deviation
IRT	Interactive Response Technology
ITT	Intention-to-treat
IVRS	Interactive voice response system
JFM	Joint frailty model
KCCQ	Kansas City Cardiomyopathy Questionnaire
LVAD	Left ventricular assist device
LDL-C	Low density lipoprotein cholesterol
LLT	Low level term
LVEF	Left ventricular ejection fraction
LVOT	Last value on treatment
LTFU	Lost to follow-up
Max	Maximum

Term	Definition / description
MedDRA	Medical Dictionary for Regulatory Activities
MI	Myocardial infarction
Min	Minimum
MMRM	Mixed models repeated measures
MRA	Mineralocorticoid Receptor Antagonist
Non-CV	Non-cardiovascular
NT pro-BNP	N-terminal pro B-type natriuretic peptide
NYHA	New York Heart Association Classification
OC-AD	Observed Case including data after discontinuation
OC-OT	Observed Case on-treatment
PK	Pharmacokinetic
PAOD	Peripheral Arterial Occlusive Disease
PT	Preferred term
Q1	Lower quartile
Q3	Upper quartile
PDMAP	Project data management and analysis plan
RS	Randomized set
SAE	Serious adverse event
SAS	Statistical Analysis System
SBP	Systolic blood pressure
SCR	Screened set
SD	Standard deviation
SE	Standard error
SGLT-1	Sodium-glucose co-transporter 1
SGLT-2	Sodium-glucose co-transporter 2
SI	Système international d'unités
SMQ	Standardized MedDRA query
SOC	System organ class
TBILI	Total bilirubin
TS	Treated set
TS-FU	Treated set – Follow-up
TSAP	Trial statistical analysis plan

Term	Definition / description
UACR	Urine Albumin Creatinine Ratio
ULN	Upper limit of normal
UTI	Urinary tract infection
WHO DD	World Health Organization Drug Dictionary

3. INTRODUCTION

As per the International Conference on Harmonisation (ICH) E9 guidance [\(1\)](#), the purpose of this document is to provide a more technical and detailed elaboration of the principal features of the analysis described in the protocol, and to include detailed procedures for executing the statistical analysis of the primary and secondary variables and other data.

This Trial Statistical Analysis Plan (TSAP) assumes familiarity with the Clinical Trial Protocol (CTP), including Protocol Amendments. In particular, the TSAP is based on the planned analysis specification as written in CTP Section 7 “Statistical Methods and Determination of Sample Size”. Therefore, TSAP readers may consult the CTP for more background information on the study, e.g., on study objectives, study design and population, treatments, definition of measurements and variables, planning of sample size, randomization.

SAS[®] Version 9.4 or later will be used for all analyses.

4. CHANGES IN THE PLANNED ANALYSIS OF THE STUDY

1. In the random coefficient model used to estimate slope in change from baseline of eGFR (CKD-EPI)_{cr}, an additional fixed effect term of interaction of eGFR (CKD-EPI)_{cr} at baseline (continuous) by time is included.
2. As per protocol the objective of the trial is “to demonstrate superiority of empagliflozin 10 mg versus placebo”.
The ITT analysis approach was chosen to as closely as possible reflect real-life conditions, disregarding any occurrences of treatment stop or restart of treatment, that may happen in clinical practice as well.
However, it is also recognized and recommended by the Executive Steering Committee that the study-specific treatment discontinuation in the close-out period does not resemble clinical practice.
Therefore for patients that complete the treatment period according to protocol after close-out announcement the time at risk for efficacy endpoints ends at the discontinuation of treatment and events occurring thereafter are not considered in the efficacy analyses.
The primary estimand is now specified in [Section 7.4](#).
An analysis including all events after randomization will be conducted as sensitivity analysis for the primary endpoint and the key secondary endpoint of recurrent HHF. A corresponding approach will be used for continuous endpoints.
3. Mixed model for repeated measures (MMRM) for KCCQ at week 52 as well as other MMRMs were specified in condensed form to be in line with BI internal standards. Therefore, individual model terms were removed from the MMRM if already included as interaction term with treatment or visit. Additionally, the terms included in MMRMs were aligned throughout the TSAP
4. The rules defining ‘win’ and ‘lose’ for the win ratio calculation were clarified and adapted to also consider the time to first HHF event in case of a tie in the number of HHF events. The adaption was made since time to first HHF event is also considered relevant information to avoid ties in case the number of HHF events is identical. This approach is a modification of the rules applied by Rogers 2014 ([8](#)).

5. ENDPOINTS

5.1 PRIMARY ENDPOINT

The primary endpoint is the composite of time to first event of adjudicated CV death or adjudicated HHF.

For further clarification: Adjudicated CV death always includes death adjudicated as death due to undetermined cause. This is applicable throughout all analyses wherever adjudicated CV death is mentioned.

5.2 SECONDARY ENDPOINTS

5.2.1 Key secondary endpoints

Key secondary endpoints are:

- Occurrence of adjudicated HHF (first and recurrent)
- eGFR (CKD-EPI)_{cr} slope of change from baseline

5.2.2 Other secondary endpoints

Other secondary endpoints are specified in the CTP Sections 5.1.2 and 5.2, and in TSAP [Section 7.5.2](#).

5.3 FURTHER ENDPOINTS

Further endpoints are listed in the CTP Section 5.1.3, and in TSAP [Section 7.6](#). The definition and assessment can be found in Section 5.2.

Further endpoints added include:

- Time to non-cardiovascular (non-CV) death (i.e. death cases not included in the definition of adjudicated CV death)
- Fasting glucose (FG) change from baseline to last value on treatment (LVOT) and follow-up (FU), overall and by status of diabetes mellitus (DM)
- Time to first investigator-defined CV hospitalization. Investigator-defined CV hospitalization includes AEs ticked by the investigator as “CV hospitalization (due to reasons other than heart failure, MI or stroke)” and AEs ticked as “Hospitalization for Heart failure” as well as events ticked as “Cardiovascular (CV) Death other than CV death attributed to myocardial infarction or stroke”, MI, stroke, non-fatal TIA that are reported as requiring hospitalization.
- Time to atrial fibrillation (defined as time to first reported ECG indicating atrial fibrillation or to first AE with PT atrial fibrillation).

5.4 OTHER VARIABLES

5.4.1 Kansas City Cardiomyopathy Questionnaire (KCCQ) scores

There are 10 summary scores within the KCCQ, which are calculated as follows:

1. Physical Limitation

Code responses to each of Questions 1a-f as follows:

- Extremely limited = 1
- Quite a bit limited = 2
- Moderately limited = 3
- Slightly limited = 4
- Not at all limited = 5
- Limited for other reasons or did not do = <missing value>

If at least three of Questions 1a-f are not missing, then the Physical Limitation Score is calculated as follows:

Physical Limitation Score = $100 * [(\text{mean of Questions 1a-f actually answered}) - 1] / 4$

2. Symptom Stability

Code the response to Question 2 as follows:

- Much worse = 1
- Slightly worse = 2
- Not changed = 3
- Slightly better = 4
- Much better = 5
- I've had no symptoms over the last 2 weeks = 3

If Question 2 is not missing, then the Symptom Stability Score is calculated as follows:

Symptom Stability Score = $100 * [(Question\ 2) - 1] / 4$

3. Symptom Frequency

Code responses to Questions 3, 5, 7 and 9 as follows:

Question 3

- Every morning = 1
- 3 or more times a week but not every day = 2
- 1-2 times a week = 3
- Less than once a week = 4
- Never over the past 2 weeks = 5

Questions 5 and 7

- All of the time = 1
- Several times a day = 2
- At least once a day = 3
- 3 or more times a week but not every day = 4
- 1-2 times a week = 5
- Less than once a week = 6
- Never over the past 2 weeks = 7

Question 9

- Every night = 1
- 3 or more times a week but not every day = 2
- 1-2 times a week = 3
- Less than once a week = 4
- Never over the past 2 weeks = 5

If at least two of Questions 3, 5, 7 and 9 are not missing, then the Symptom Frequency Score is calculated as follows:

$$S3 = [(Question\ 3) - 1]/4$$

$$S5 = [(Question\ 5) - 1]/6$$

$$S7 = [(Question\ 7) - 1]/6$$

$$S9 = [(Question\ 9) - 1]/4$$

Symptom Frequency Score = $100 * (\text{mean of S3, S5, S7 and S9})$

4. Symptom Burden

Code responses to each of Questions 4, 6 and 8 as follows:

- Extremely bothersome = 1
- Quite a bit bothersome = 2
- Moderately bothersome = 3
- Slightly bothersome = 4
- Not at all bothersome = 5
- I've had no swelling/fatigue/shortness of breath = 5

If at least one of Questions 4, 6 and 8 is not missing, then the Symptom Burden Score is defined as follows:

Symptom Burden Score = $100 * [(\text{mean of Questions 4, 6 and 8 actually answered}) - 1] / 4$

5. Total Symptom Score

The Total Symptom Score is defined as the mean of the following available summary scores:

Symptom Frequency Score and Symptom Burden Score

6. Self-Efficacy

Code responses to Questions 10 and 11 as follows:

Question 10

- Not at all sure = 1
- Not very sure = 2
- Somewhat sure = 3
- Mostly sure = 4
- Completely sure = 5

Question 11

- Do not understand at all = 1
- Do not understand very well = 2

- Somewhat understand = 3
- Mostly understand = 4
- Completely understand = 5

If at least one of Questions 10 and 11 is not missing, then the Self-Efficacy Score is calculated as:

$$\text{Self-Efficacy Score} = 100 * [(\text{mean of Questions 10 and 11 actually answered}) - 1] / 4$$

7. Quality of Life

Code responses to Questions 12, 13 and 14 as follows:

Question 12

- It has extremely limited my enjoyment of life = 1
- It has limited my enjoyment of life quite a bit = 2
- It has moderately limited my enjoyment of life = 3
- It has slightly limited my enjoyment of life = 4
- It has not limited my enjoyment of life at all = 5

Question 13

- Not at all satisfied = 1
- Mostly dissatisfied = 2
- Somewhat satisfied = 3
- Mostly satisfied = 4
- Completely satisfied = 5

Question 14

- I felt that way all of the time = 1
- I felt that way most of the time = 2
- I occasionally felt that way = 3
- I rarely felt that way = 4
- I never felt that way = 5

If at least one of Questions 12, 13 and 14 is not missing, then the Quality of Life Score is calculated as:

$$\text{Quality of Life Score} = 100 * [(\text{mean of Questions 12, 13 and 14 actually answered}) - 1] / 4$$

8. Social Limitation

Code responses to each of Questions 15a-d as follows:

- Severely limited = 1
- Limited quite a bit = 2
- Moderately limited = 3
- Slightly limited = 4
- Did not limit at all = 5
- Does not apply or did not do for other reasons = <missing value>

If at least two of Questions 15a-d are not missing, then the Social Limitation Score is calculated as:

$$\text{Social Limitation Score} = 100 * [(\text{mean of Questions 15a-d actually answered}) - 1] / 4$$

9. Overall Summary Score

The Overall Summary Score is defined as the mean of the following available summary scores:

Physical Limitation Score, Total Symptom Score, Quality of Life Score and Social Limitation Score

10. Clinical Summary Score

The Clinical Summary Score is defined as the mean of the following available summary scores:

Physical Limitation Score and Total Symptom Score

Note: references to “means of questions actually answered” imply the following.

If there are n questions in a scale, and the subject must answer m to score the scale, but the subject answers only n-i, where n-i >= m, calculate the mean of those questions as

(sum of the responses to those n-i questions) / (n-i)

not

(sum of the responses to those n-i questions) / n

Patient-preferred outcome is derived from response to the question about which domain is the most difficult for the patient to cope with at baseline:

- Loss of functional abilities: Physical Limitation Score
- Symptoms due to your heart failure: Total Symptom Score
- Your concern about how to manage your heart failure: Self-Efficacy Score
- Suffering from depression, anxiety, emotional liability because you have heart failure: Quality of Life Score
- Adapting your life to heart failure: Social Limitation Score

5.4.2 LVEF

Values of LVEF will be considered valid, when appropriate methodology was used. When methodology is missing, LVEF will be disregarded.

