6.6 HANDLING OF MISSING DATA AND OUTLIERS

6.6.1 Imputation methods

There will be no imputation of data for safety analyses. For patients who discontinue the trial treatment prematurely, all efforts will be made to follow patients for survival and for any other endpoints including the primary and key secondary endpoints until the end of the trial.

There will be different methods of looking at continuous longitudinal data.

Observed case on-treatment (OC-OT):

Only the available data that were observed while patients were on study medication (defined as time from first drug intake until last permanent treatment stop date plus the endpoint specific follow-up time (as defined in [Table 6.1:2](#)) are considered.

Measurements are assigned to planned weeks according to [Table 6.7: 1](#)

Observed case including data after treatment discontinuation (OC-AD):

All available data are considered, including values obtained on treatment or post-treatment.

Measurements are assigned to planned weeks according to [Table 6.7: 1](#).

As described in [Section 4](#), for patients that completed the treatment phase as planned (primary reason for end of treatment being completion of treatment period according to protocol), measurements after last study drug intake should not be considered. Therefore for those patients, any data after the endpoint specific follow-up time (as defined in [Table 6.1:2](#)) will not be included in the OC-AD analysis.

KCCQ imputation

If not otherwise noted, for endpoints of KCCQ scores, for patients who die, a worst score (score of 0) will be imputed for the score at all subsequent scheduled visits after the date of death where the score would have been assessed.

Multiple imputations:

A multiple imputations approach will be considered to impute missing data. Multiple imputation approaches taken are further specified in [Section 7](#) with the planned sensitivity analyses.

Imputation of missing covariates in multivariate Cox regression models and for recurrent event analyses

To avoid excluding patients from Cox regression analyses due to missing covariates, the overall population median of the corresponding variable will be imputed for continuous covariates and the most frequent category will be imputed for categorical covariates.

No imputation will be done for covariates included in treatment by subgroup interaction terms.

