The number of HHF events per patient will be summarized descriptively. Additionally a negative binomial model will be fitted to the data of recurrent HHF. This will be done once including only treatment as covariate and once including all covariates as the primary model. Rate ratio and confidence intervals of both models will be reported.

The mean cumulative incidence will be displayed for adjudicated recurrent HHF.

Subgroup analyses will be explored as outlined in [Section 6.4](#) for adjudicated recurrent HHF. For subgroup analyses the term of subgroup (if not already part of the model) and subgroup by treatment will be added to the model of the recurrent event. If the subgroup variable is a categorization of a continuous covariate, this covariate will be dropped from the subgroup model.

eGFR (CKD-EPI)_{cr} slope of change from baseline

Slope in change from baseline of eGFR (CKD-EPI)_{cr} will be analysed by a random coefficient model allowing for random intercept and random slope per patient. The model will include the factors treatment, sex, geographical region, and status of DM as fixed effects and eGFR (CKD-EPI)_{cr} at baseline (continuous), LVEF (continuous), age (continuous), time and interaction of treatment by time and interaction of eGFR (CKD-EPI)_{cr} at baseline

(continuous) by time as linear covariates and allow for randomly varying slope and intercept between patients. The model will include all on-treatment change from baseline data.

Since the slope is run on the change from baseline data, the intercept will model the acute drop, whereas the long-term effect is modelled by the slope.

A plot of individual patient slopes and separately of individual patient intercepts will be provided per treatment and by eGFR at baseline.

Subgroup analyses as outlined in [Section 6.4](#) will be explored for eGFR slope. The subgroup model will include additionally to the model described above, the subgroup if not already part of the model, subgroup by treatment and subgroup by treatment by time. If the subgroup variable is a categorization of a continuous covariate, this covariate will be dropped from the subgroup model.

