Change from baseline in clinical summary score for HF symptoms and physical limitations domains of the KCCQ at week 52 will be evaluated by a mixed model for repeated measures (MMRM) including LVEF (continuous), age (continuous) and eGFR (CKD-EPI)_{cr} at baseline (continuous) as linear covariates and, baseline score by visit, visit by treatment, sex, geographical region and status of diabetes at baseline as fixed effects. An additional factor of “week reachable” for the parameter in question, which for each patient is the theoretically reachable planned measurement based on the time of randomisation will adjust for the different planned study times.

All on-treatment data up to week 52 will be included and the analysis will be conducted on the treated set.

A sensitivity analysis will be conducted including data after discontinuation (OC-AD) on the randomized set.

An additional analysis will be performed for the Clinical Summary Score on OC-AD without imputing a worst score for patients who die.

- *Occurrence of all-cause hospitalisation (first and recurrent)*

A similar joint frailty model as well as negative binomial regression model as in the HHF will be analysed for all-cause hospitalization. Instead of CV death, all-cause mortality will be jointly modelled as the terminal events in the joint frailty model.

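### LVEF with no recorded method is set aside, but missing covariates are imputed only for Cox and recurrent-event models, so the confirmatory eGFR slope model needlessly omits treated patients without a valid LVEF

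*SAP*

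**What the plan says.** All references are to the revised SAP (last revision 12 February 2021).

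- Section 5.4.2 accepts an LVEF value only if it was obtained by a suitable method, and adds: "When methodology is missing, LVEF will be disregarded".
- Section 6.6.1 has one rule for missing covariates, under the heading "Imputation of missing covariates in multivariate Cox regression models and for recurrent event analyses". Its purpose is given as "To avoid excluding patients from Cox regression analyses due to missing covariates". The method is that "the overall population median of the corresponding variable will be imputed for continuous covariates", with the most frequent category for categorical ones. Covariates in treatment-by-subgroup interactions are not imputed.
- Section 7.5.1: "Slope in change from baseline of eGFR (CKD-EPI)_{cr} will be analysed by a random coefficient model". Its linear covariates include "LVEF (continuous), age (continuous), time and interaction of treatment by time". The section says the model takes in every on-treatment change from baseline. Section 7.4.1 places the slope third in the testing hierarchy, with 0.001 of alpha at the final analysis.
- Section 7.5.2 adjusts the week-52 KCCQ model for continuous LVEF and says: "All on-treatment data up to week 52 will be included and the analysis will be conducted on the treated set".
- Section 7.6 includes LVEF in the further MMRMs, the ANCOVAs and the KCCQ responder logistic models. The laboratory and heart-rate models in Sections 7.8.2 and 7.8.3 follow the same specifications.

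**The concern.** The plan's own validity rule can make a covariate missing. Its own safeguard against losing patients for that reason then stops at the Cox and recurrent-event models. A linear mixed model, ANCOVA or logistic regression fitted by standard likelihood software leaves out any record with a missing covariate. When the covariate is a baseline value, the patient's whole series goes.

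A treated patient with complete eGFR follow-up but no usable LVEF would therefore count in steps 1 and 2 of the hierarchy and contribute nothing to step 3. What is at stake is information in a confirmatory test run at a strict level, and the clarity of who is analysed in it. If the plan is silent, that choice is made at programming.

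**Working it through.** **Does any other provision close the gap?**

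1. *IRT data.* Section 6.4 uses IRT information to assign subgroup categories. It does not supply a continuous model covariate.
2. *Multiple imputation.* Section 6.6.1 refers to the sensitivity analyses in Section 7. There the current text uses it for the primary endpoint only (7.4.2). The history table explains that it was dropped for the slope because it is asymptotically equivalent to maximum likelihood under missing at random. That argument concerns missing outcomes, not patients left out for a missing covariate.
3. *Another measurement.* Section 6.7 takes the last available pre-treatment value as baseline. A patient with a second, valid pre-treatment LVEF need not be lost. A patient without one is.
4. *Other covariates.* Diabetes status has a fallback definition (Table 9.3: 1) and region follows the IRT assignment (9.1). LVEF is the covariate that the plan itself may set aside.

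Nothing closes it.

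**Size**

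The SAP states no figure for voided LVEF or for slope power, so there is none to reproduce on this point. The inputs from the document are about 5750 planned patients (9.6) and alpha 0.001 for the slope (7.4.1). The share *f* of patients without a valid LVEF is an assumption.

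- Patients lost = 5750 × *f*.
- Standard error ratio = 1/√(1 − *f*), if these patients carry average information.
- Power = Φ[(z₀.₉₉₉₅ + z_p)·√(1 − *f*) − z₀.₉₉₉₅], where z₀.₉₉₉₅ = 3.29 and p is an assumed full-data power of 90% (z_p = 1.28) or 80%.

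| *f* (assumed) | Patients lost | SE increase | Power if 90% | Power if 80% |
|---|---|---|---|---|
| 0.5% | 29 | 0.25% | 89.8% | 79.7% |
| 1% | 58 | 0.5% | 89.6% | 79.4% |
| 2% | 115 | 1.0% | 89.2% | 78.8% |
| 5% | 288 | 2.6% | 87.8% | 76.9% |
| 10% | 575 | 5.4% | 85.2% | 73.6% |

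Example at 1%: 1/√0.99 = 1.005, and Φ(4.57 × 0.995 − 3.29) = Φ(1.26) = 89.6%. The counts use planned randomised patients. The slope uses treated patients, so the true counts would be slightly lower.

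**Mechanism check.** A random-coefficient model was fitted to simulated data on 400 patients, with LVEF removed for 20 of them (5%). The complete-case fit kept 380 patients, and the standard error of treatment by time was 0.285. With median imputation all 400 were kept and it was 0.278, the same as with full data. The ratio 0.285/0.278 = 1.025 agrees with the formula's 1.026.

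**The case against.** The best defence is that this is a small wording gap. Several parts of it stand.

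- The SAP nowhere says that these patients are excluded. The omission follows from ordinary model fitting. Section 6.6.1, however, recognises the same mechanism for Cox models, so the inference is secure.
- Section 5.4.2 voids a value, not a patient. One blank method field does not remove everyone it touches, because another valid pre-treatment value may exist.
- The number is probably small. Ejection fraction is an entry criterion, and failing it is an important deviation (A1.07, Table 6.2: 1).
- Only the slope is confirmatory. Section 7.5.2 calls the other secondary endpoints, KCCQ included, exploratory. The Section 7.6 ANCOVAs are already limited to patients with valid baseline, last on-treatment and follow-up values.
- Stating that complete-case analysis is intended would also remove the ambiguity. It would not recover the lost data.

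A reader might infer four stronger points, which the document does not support:

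- *The gap is why the hierarchy is tested on different patients.* Steps 1 and 2 use data up to the end of the planned treatment phase, including data after premature stopping. Step 3 uses on-treatment eGFR. They differ by design, and closing this gap would not make them the same.
- *Every efficacy model is affected.* The treatment-only Cox and negative binomial models and the win ratio contain no LVEF.
- *The loss clusters at certain sites.* The SAP has no information on this.
- *The slope estimate is biased.* LVEF and its method are baseline information, and nothing points to a difference by arm.

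**Conclusion.** The point holds as an avoidable loss of precision in one confirmatory model, with the same gap in several exploratory ones. The plan can void LVEF, adjusts the eGFR slope for it, and confines its covariate rule to other models. As written, the slope model omits treated patients who have usable eGFR data but no valid LVEF, contrary to its stated data scope.

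The number of such patients is unknown. Per assumed 1%, the slope standard error rises by about 0.5%, and an assumed 90% power at alpha 0.001 falls to 89.6%. At an assumed 5% it falls to 87.8%. These figures rest on the assumed share, the assumed full-data power, and average information per lost patient. The effect is modest, but nothing is gained by accepting it.

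**What to change.** Extend the heading and sentence in Section 6.6.1 so that the median or most-frequent-category rule also covers missing non-outcome baseline covariates in the eGFR slope model and the other covariate-adjusted efficacy models (MMRM, ANCOVA, KCCQ logistic). Do not extend it to the baseline of the outcome itself, because the change from baseline is then undefined. Keep the existing no-imputation rule for covariates in treatment-by-subgroup interactions. Report by arm the number of voided LVEF values.

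Section 6.6.1 also rules out imputation in safety analyses. The text should therefore say whether the laboratory and heart-rate models in Sections 7.8.2 and 7.8.3 are meant to stay complete-case.

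The cost is a short text change made before unblinding, reusing covariates already derived for the Cox models. The rule uses overall, not arm-specific, values of baseline variables, so there is essentially no downside.
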